**Table 6-7. MLN9708 and Lenalidomide Dose Modification for Neutropenia**

Absolute Neutrophil Count	Action
First fall to $< 1,000/\text{mm}^3$	Interrupt lenalidomide treatment, follow CBC weekly
Returns to $\geq 1,000/\text{mm}^3$ within the same cycle	Resume lenalidomide at 15 mg
Second fall: Subsequent drop below $1,000/\text{mm}^3$	Interrupt MLN9708, follow CBC weekly
Returns to $\geq 1,000/\text{mm}^3$ within the same cycle	Resume MLN9708 at reduced dose by 1 level (Level 1)
Third fall: Subsequent drop below $1,000/\text{mm}^3$	Interrupt lenalidomide treatment, follow CBC weekly
Returns to $\geq 1,000/\text{mm}^3$ within the same cycle	Resume lenalidomide at 10 mg
Fourth fall: Subsequent drop below $1,000/\text{mm}^3$	Interrupt MLN9708, follow CBC weekly
Returns to $\geq 1,000/\text{mm}^3$ within the same cycle	Resume MLN9708 at reduced dose by 1 level (Level 2)
	Do not dose MLN9708 below 2.3 mg
Fifth fall: Subsequent drop below $1,000/\text{mm}^3$	Interrupt lenalidomide, follow CBC weekly
Returns to $\geq 1,000/\text{mm}^3$ within the same cycle	Resume lenalidomide at 5 mg
	Do not dose lenalidomide below 5 mg

CBC = complete blood count

### **6.5.2.3 Dose Modification for Non-hematological Toxicity**

#### **6.5.2.3.1 Dose Modification for Rash**

If Grade 2 or 3 rash occurs in Cycle 2 or subsequent cycles, lenalidomide dose should be interrupted. If the rash is recovered to Grade 1 or lower within 2 weeks, lenalidomide may be reinitiated with one dose level reduction. MLN9708 dose can be kept as is. If rash occurs more than once, MLN9708 or lenalidomide dose will be reduced according to [Table 6-8](#) to continue the treatment. In some severe situations, both lenalidomide and MLN9708 may be interrupted or reduced if needed based on discussion between the investigator and the sponsor.

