#### **1.4.2 Clinical Studies in Patients With Newly Diagnosed Multiple Myeloma**

Two ongoing clinical trials of Studies C16005 and C16006 in patients with newly diagnosed multiple myeloma are currently ongoing.

In Study C16005 where MLN9708 is administered weekly (1.68, 2.23, 2.97, and 3.95 mg/m^2) in combination with lenalidomide and dexamethasone (Rd), 15 patients have been enrolled as of 12 October 2011 and completed 1 to 9 treatment cycles (median, 5 cycles). No DLTs were seen at doses up to 2.23 mg/m^2. Three of 3 patients treated at the 3.95 mg/m^2 dose cohort experienced Grade 3 nausea and vomiting despite adequate antiemetic therapy; one of which additionally experienced Grade 2 syncope and in another patient the dose of lenalidomide was compromised such that they received < 80% of the planned doses. Subsequent patients were treated at one dose level below (2.97 mg/m^2) where one of 6 patients experienced a DLT (Grade 3 rash). The MTD of weekly MLN9708 in combination with Rd was established at 2.97mg/m^2. However with this dose, 3 of 6 patients experienced Grade 2 and 3 rash and had to discontinue lenalidomide. Therefore, the recommended dose was determined to be 2.23 mg/m^2 plus Rd in the phase 2 portion of the combination trial and phase 3 Rd combination trial.

To date, all 15 response-evaluable patients have achieved ≥ PR to therapy including 4 CRs, 4 VGPRs, and 7 PRs; 14 out of 15 patients achieved ≥ PR after Cycle 1, and all 15 achieved ≥ PR after Cycle 2.

Overall, all 15 patients experienced a treatment-emergent adverse event. Peripheral neuropathy was limited to Grade 1 or 2 in 3 patients. The most common (≥ 20%) treatment-emergent adverse events are shown in [Table 1-5](#).

**Table 1-5. Most Common ( $\geq 20\%$ ) Treatment-Emergent Adverse Events  
(Study C16005, N=15)**

	Treatment-Emergent Adverse Events
Most Common ( $\geq 20\%$ ) Any Grade	Fatigue (60%) Vomiting (53%) Anemia (40%) Diarrhea and nausea (33% each) Insomnia, peripheral edema, and thrombocytopenia (27% each)
Drug-Related Grade $\geq 3$ in $\geq 2$ Patients	Rash and vomiting (n = 2 each)

Data cutoff 12 October 2011

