**Table 6-8. MLN9708 and Lenalidomide Dose Modification for Rash**

Rash	Action
Grade 2 or 3	Interrupt lenalidomide treatment
Recovers to < Grade 2 within 2 weeks	Resume lenalidomide at 15 mg
If does not recover to < Grade 2 in 2 weeks	Interrupt MLN9708
OR for subsequent occurrence of Grade 2 or 3 rash	
Recovers to < Grade 2 within 2 weeks	Resume MLN9708 at reduced dose by 1 level (Level 1)
If does not recover to < Grade 2 in 2 weeks	Interrupt lenalidomide treatment
OR for subsequent occurrence of Grade 2 or 3 rash	
Recovers to < Grade 2 within 2 weeks	Resume lenalidomide at 10 mg
If does not recover to < Grade 2 in 2 weeks	Interrupt MLN9708
OR for subsequent occurrence of Grade 2 or 3 rash	
Recovers to < Grade 2 within 2 weeks	Resume MLN9708 at reduced dose by 1 level (Level 2)
	Do not dose MLN9708 below 2.3 mg
If does not recover to < Grade 2 in 2 weeks	Interrupt lenalidomide treatment
OR for subsequent occurrence of Grade 2 or 3 rash	
Recover to < Grade 2 within 2 weeks	Resume lenalidomide at 5 mg
	Do not dose lenalidomide below 5 mg

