**6.5.2.3.2 MLN9708 Treatment Modification**

MLN9708 dose adjustments are allowed based on clinical and laboratory findings. Dose reduction levels of MLN9708 for toxicity are indicated in [Table 6-5](#). Treatment modifications due to MLN9708-related non-hematological toxicities are outlined in [Table 6-9](#).

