**Table 6-9. MLN9708 Treatment Modification Due to Non-hematological Toxicities**

Adverse Event (Severity)	Action on MLN9708	Further Considerations
Grade 2 peripheral neuropathy with pain	

• Hold MLN9708 until resolution to Grade <math>\leq</math> 1 or baseline

• MLN9708 may be reinitiated with one dose level reduction.

	
Grade 3 non-hematological toxicity	

• Hold MLN9708 until resolution to Grade <math>\leq</math> 1 or baseline

• MLN9708 may be reinitiated with one dose level reduction

	
Grade 4 non-hematological toxicities	

• Consider permanently discontinuing MLN9708

	With agreement by the sponsor, investigators may consider restarting the therapy for patients continue to benefit from the therapy

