**Table 6-10. Lenalidomide Treatment Modification Guidelines Due to Non-hematological Toxicities**

Adverse Event (Severity)	Action on Lenalidomide	Further Considerations
Grade 3/4 toxicities judged to be related to lenalidomide (other than the toxicities listed below)	
 
Hold lenalidomide treatment, and restart at the next lower dose level when toxicity has resolved to <math>\leq</math> Grade 2
 
	Do not dose below 5 mg
Renal dysfunction	
 
Dose reduction, interruption, or discontinuation per lenalidomide package insert
 
	Care should be taken in dose selection/modification in the elderly as they are more likely to have decreased renal function  Monitor renal function regularly
$\geq$ Grade 2 thrombosis/embolism	
 
Hold lenalidomide and start anticoagulation therapy; restart at investigator's discretion after adequate anticoagulation; maintain dose level (No dose modification)
 
	For patients treated with Rd, thromboprophylaxis such as aspirin according to the institutional standard of care is recommended
Angioedema, Stevens-Johnson Syndrome (SJS), and Toxic Epidermal Necrolysis (TEN)		
Grade 2/3 skin rash	
 
Hold or discontinue lenalidomide
 
	
Grade 4 exfoliative or bullous rash or if SJS or TEN suspected	
 
Permanently discontinue lenalidomide
 
	
Any grade angioedema	
 
Permanently discontinue lenalidomide
 
	
Any grade tumor Lysis syndrome	
 
Hold lenalidomide in the same cycle. Upon recovery, lenalidomide can be restarted at the same dose used before interruption.
 
	Monitor closely and take appropriate medical precautions.

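### In the Rd cohorts from Cycle 2, a first Grade 3 rash judged related to MLN9708 falls under two differing MLN9708 rules, and the protocol does not say which governs

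*Protocol*

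**What the plan says.** Three places in Protocol 6.5.2 deal with rash in the Rd cohorts.

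- **6.5.2.3.1 and Table 6-8.** The rule opens: "If Grade 2 or 3 rash occurs in Cycle 2 or subsequent cycles, lenalidomide dose should be interrupted". For MLN9708 it adds "MLN9708 dose can be kept as is". If the rash falls below Grade 2 within 2 weeks, the lenalidomide step in Table 6-8 is "Resume lenalidomide at 15 mg". Table 6-8 interrupts MLN9708 only if the rash has not recovered in 2 weeks or comes back. The section closes with a discretionary clause: "In some severe situations, both lenalidomide and MLN9708 may be interrupted or reduced if needed based on discussion between the investigator and the sponsor".
- **6.5.2.3.2 and Table 6-9.** The scope is set by "Treatment modifications due to MLN9708-related non-hematological toxicities are outlined in" Table 6-9. For a Grade 3 event, that table holds MLN9708 until Grade 1 or less or baseline, after which "MLN9708 may be reinitiated with one dose level reduction". Rash is not excepted.
- **Table 6-10.** A row for Grade 2/3 skin rash, placed under the heading for angioedema, Stevens-Johnson syndrome (SJS) and toxic epidermal necrolysis (TEN), reads "Hold or discontinue lenalidomide". It gives no restart dose and no time limit.

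Two general rules stand in 6.5.2.1. Where several toxicities are present, the guideline for the most severe one applies. Each event should, where possible, be attributed to one drug so that the dose of that drug can be modified.

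**The concern.** Rash is a foreseeable event here. Section 1.5.1 lists it as a known MLN9708 risk, and 1.4.2 reports that in Study C16005, at the MTD of 2.97 mg/m2 plus Rd, "3 of 6 patients experienced Grade 2 and 3 rash and had to discontinue lenalidomide". That finding led to the lower recommended dose.

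If two rules cover the same Grade 3 rash and differ on MLN9708, two sites can each follow the protocol and give different treatment: one continues MLN9708 unchanged, the other holds it and restarts one level lower. This is a safety inconsistency. It also reaches the results, because SAP 9.4.1 tabulates doses held, reduced and discontinued, with reasons, and relative dose intensity for each drug. In cohorts of 3 to 6 subjects, those figures would partly reflect which table the investigator opened.

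**Working it through.** The plan states no figure for this point, and 10.2 says the sample size has no statistical rationale. The check is a comparison of text, followed by an illustration of size.

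**1. Which events meet both rules?** 6.5.2.3.1 is triggered by grade (2 or 3) and cycle (2 onward), with no attribution condition. Table 6-9 is triggered by Grade 3 and relatedness to MLN9708. The overlap is a Grade 3 rash, from Cycle 2, related to MLN9708 alone or to both drugs. Grade 2 rash, and rash attributed only to lenalidomide, lie outside Table 6-9.

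**2. What does each rule say for that event?**

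| | 6.5.2.3.1 / Table 6-8, first occurrence | Table 6-9 / Table 6-10 |
|---|---|---|
| MLN9708 | May continue unchanged | Table 6-9: hold; may restart one level lower |
| Lenalidomide | Interrupt; 15 mg on recovery within 2 weeks | Table 6-10: hold or discontinue; no restart rule |

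**3. Does anything else settle it?**
- The most-severe rule in 6.5.2.1 is for several toxicities, not one toxicity under several tables.
- Attribution settles only the rash attributed solely to lenalidomide. It is asked for only where possible, and 6.3.2 has the two drugs taken together.
- The severe-situations clause names no grade and depends on a discussion with the sponsor.
- Table 6-10 excludes its own listed toxicities from its general row. Table 6-9 has no such exclusion.

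**4. How many subjects?** Drug-related Grade 3 or higher rash in C16005 was 2 of 15 (Table 1-5): 6 × 2/15 = 0.8 subjects in a cohort of 6, and 3 × 2/15 = 0.4 in a cohort of 3. The rate is not limited to Cycle 2 onward. One subject of 6 is 1/6 = 17 percentage points.

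**5. What happens to exposure in one subject?** SAP 9.4.1.1: relative dose intensity (RDI) = total dose taken / total dose expected per initial dose × 100. Assumptions, not from the documents: the rash is found before the Cycle 2 Day 8 dose, recovers within 2 weeks and does not recur; 12 cycles are given (36 MLN9708 doses); there are no other changes. Four MLN9708 doses precede the hold.

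- 4.0 mg, kept: 36 × 4.0 = 144 mg; 144/144 = 100%.
- 4.0 mg, two doses held, then 3.0 mg: 4 × 4.0 + 30 × 3.0 = 106 mg; 106/144 = 73.6%. With no dose missed: 4 × 4.0 + 32 × 3.0 = 112 mg; 77.8%.
- 5.5 mg, kept: 36 × 5.5 = 198 mg; 198/198 = 100%.
- 5.5 mg, two doses held, then 4.0 mg: 4 × 5.5 + 30 × 4.0 = 142 mg; 142/198 = 71.7%. With no dose missed: 4 × 5.5 + 32 × 4.0 = 150 mg; 75.8%.
- Lenalidomide expected: 25 × 21 × 12 = 6300 mg. Taken before the rash: 25 × 28 = 700 mg. Rest of Cycle 2 held, then 15 mg: 700 + 15 × 210 = 3850 mg; 61.1%. Discontinued: 700/6300 = 11.1%, if all 12 cycles stay in the denominator.

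Dosing compliance would not show the MLN9708 difference. Its expected dose leaves out held days and uses the scheduled level, so the 4.0 mg hold path gives 106/106 = 100%.

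**The case against.** The best reply is that this is a permission beside an instruction. The wording on MLN9708 in 6.5.2.3.1 is permissive, so a site that holds MLN9708 under Table 6-9 breaches nothing in it. Rash also has its own section and stepwise table, which suggests that the specific rule governs. Attribution separates many cases, and the severe-situations clause leaves room for judgment. All of this narrows the point without removing it. The hold in Table 6-9 is not permissive, so a site that continues MLN9708 under 6.5.2.3.1 departs from Table 6-9. No passage gives the specific rule precedence.

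The reply is stronger on lenalidomide. A reader might infer that Tables 6-8 and 6-10 contradict each other. They do not quite: holding and interrupting are the same action, and the row in Table 6-10 sits under the angioedema/SJS/TEN heading, so it may be meant more narrowly. What remains is an added option to discontinue and a missing restart rule.

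A reader might also take the 3 of 6 rashes in C16005 as showing that hold or reduction rates could move by 50 points. The documents do not support that. The count mixes Grade 2 with Grade 3, and Table 6-9 would reach only Grade 3 rash. It is not limited to Cycle 2 onward, comes from newly diagnosed patients, and belongs to the dose equivalent to Cohort 4, which may not be run.

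The extra exposure during a rash is also bounded. Table 6-8 allows at most two further weekly MLN9708 doses within the 2 weeks, and only if onset precedes the Day 8 dose. Day 22 is skipped, and 6.4.2 bars a new cycle until related non-hematological toxicity is Grade 1 or less or back to baseline.

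**Conclusion.** The point holds within these limits: Rd cohorts, Cycle 2 onward, first Grade 3 rash, judged related to MLN9708 alone or with lenalidomide. For that event the protocol gives two differing instructions on MLN9708 and no precedence. The lenalidomide difference is a secondary ambiguity.

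The size is modest in numbers. At 2 of 15, fewer than one affected subject is expected in a cohort of 6, though one such subject moves a hold or reduction rate by 17 points. In the illustration, that subject's MLN9708 RDI is 100% or about 72 to 78% depending on the rule. These RDI values rest on the assumed onset, recovery and 12-cycle course.

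A reader might infer that the DLT results or cohort transitions are at risk. They are not: DLT assessment runs through Cycle 1, where these rules do not apply and 6.7.3 sets its own interruption rule. The reporting effect is confined to descriptive exposure and discontinuation summaries. The inconsistency in patient management is the main reason to act.

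**What to change.** Reconcile 6.5.2.3.1 with Table 6-8, Table 6-9 and the Grade 2/3 skin rash row of Table 6-10. State which table governs each grade of rash for each drug, and whether that depends on attribution, including rash attributed to both drugs. In the other tables, exclude rash by cross-reference, as Table 6-10 already does for its own listed toxicities. State whether the Table 6-10 row is meant only for rash in the angioedema/SJS/TEN context, and make its restart position consistent with Table 6-8. Which action applies is for the sponsor's clinical team to decide.

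The cost is a wording amendment to one section and three tables. It needs no added visits, data or analyses.

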**Table 6-8. MLN9708 and Lenalidomide Dose Modification for Rash**

Rash	Action
Grade 2 or 3	Interrupt lenalidomide treatment
Recovers to < Grade 2 within 2 weeks	Resume lenalidomide at 15 mg
If does not recover to < Grade 2 in 2 weeks	Interrupt MLN9708
OR for subsequent occurrence of Grade 2 or 3 rash	
Recovers to < Grade 2 within 2 weeks	Resume MLN9708 at reduced dose by 1 level (Level 1)
If does not recover to < Grade 2 in 2 weeks	Interrupt lenalidomide treatment
OR for subsequent occurrence of Grade 2 or 3 rash	
Recovers to < Grade 2 within 2 weeks	Resume lenalidomide at 10 mg
If does not recover to < Grade 2 in 2 weeks	Interrupt MLN9708
OR for subsequent occurrence of Grade 2 or 3 rash	
Recovers to < Grade 2 within 2 weeks	Resume MLN9708 at reduced dose by 1 level (Level 2)
	Do not dose MLN9708 below 2.3 mg
If does not recover to < Grade 2 in 2 weeks	Interrupt lenalidomide treatment
OR for subsequent occurrence of Grade 2 or 3 rash	
Recover to < Grade 2 within 2 weeks	Resume lenalidomide at 5 mg
	Do not dose lenalidomide below 5 mg

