#### **6.4.2 MLN9708 in Combination With Rd**

Treatment of MLN9708 with Rd will be repeated every 28 days as 1 cycle. For a new treatment cycle to begin, the patient must satisfy the following criteria:

- ANC must be  $\geq 1,000 \text{ mm}^3$
- Platelet count must be  $\geq 75,000 \text{ mm}^3$
- All other nonhematological toxicities (except for alopecia) considered related to MLN9708 or Rd must be resolved to  $\leq$  Grade 1 or to the patient's baseline values

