#### **6.4.3 Criteria for Dose Delays**

If a subject fails to meet the criteria for beginning the next cycle of treatment, initiation of the next cycle should be delayed for one week for re-evaluation. If the subject still fails to meet the criteria, the subject should be re-evaluated weekly. The next cycle treatment can be initiated if the subject meets the criteria for initiating the next cycle within 3 weeks of the scheduled initiation of the next cycle. The MLN9708 and lenalidomide starting doses for the next cycle are presented below.

- Reinitiate with one dose level reduction
  - If MLN9708 or lenalidomide treatment was interrupted during the preceding cycle in accordance with “[6.5 Dose Modification](#)” and treatment could not be resumed within the same cycle
- Reinitiate with the same dose level as the preceding cycle
  - If there was no need for dose adjustment in the preceding cycle
  - If MLN9708 or lenalidomide treatment was interrupted during the preceding cycle in accordance with “[6.5 Dose Modification](#)” and treatment could be resumed during the cycle

Should the start of the next cycle need to be delayed for more than 3 weeks because of incomplete recovery from treatment-related toxicity, the patient undergoes the EOS exams, and treatment should be discontinued.

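### Table 6-8 uses the same rows for recurrent and unresolved rash: on the unresolved path it re-interrupts drugs already held, restarts only one of two, and gives restart doses that differ from section 6.4.3

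*Protocol*

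**What the plan says.** Protocol 6.5.2.3.1 sets the first step: "If Grade 2 or 3 rash occurs in Cycle 2 or subsequent cycles, lenalidomide dose should be interrupted". If the rash settles within 2 weeks, lenalidomide restarts one level lower and MLN9708 is unchanged. The section then sends the reader to Table 6-8 for repeat events only: "If rash occurs more than once, MLN9708 or lenalidomide dose will be reduced according to" that table.

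Table 6-8 is a five-step ladder. Steps 1, 3 and 5 say "Interrupt lenalidomide treatment"; steps 2 and 4 say "Interrupt MLN9708". Steps 2 to 5 each have two alternative triggers, "If does not recover to < Grade 2 in 2 weeks" and "OR for subsequent occurrence of Grade 2 or 3 rash". The recovery rows after steps 1 to 5 give, in order: lenalidomide 15 mg, MLN9708 Level 1, lenalidomide 10 mg, MLN9708 Level 2, lenalidomide 5 mg. Each names one drug. No row covers failure to recover after step 5.

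Two rules outside the rash section also apply to the Rd cohorts:

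- Section 6.4.2, for starting a new cycle: "All other nonhematological toxicities (except for alopecia) considered related to MLN9708 or Rd must be resolved to" Grade 1 or lower, or baseline.
- Section 6.4.3, for delays. A drug interrupted under 6.5 and not resumed in the same cycle restarts one dose level lower. The section also has a limit: "Should the start of the next cycle need to be delayed for more than 3 weeks because of incomplete recovery from treatment-related toxicity", the patient has the end-of-study examinations and treatment stops. Section 6.6.2 repeats the limit.

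**The concern.** Recurrence and non-recovery leave the patient in different states. After a recurrence, the drug named in the row has normally been restarted, so interrupting it means something. After non-recovery nothing has been restarted, so from step 3 on the row interrupts a drug already on hold, and its recovery line says nothing about the other held drug.

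The later rows also fall where the next-cycle rule in 6.4.3 applies, and that rule sets its own restart doses. The rash section does not say which prevails. The haematological sections (6.5.2.2.1 and 6.5.2.2.2, Tables 6-6 and 6-7) limit resumption to the same cycle and refer to 6.4; the rash section does neither.

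At stake are the MLN9708 and lenalidomide doses given after a long rash. The summaries in SAP 9.4.1 built on them (dose intensity, relative dose intensity, doses held and reduced) would partly reflect which rule a site followed. So could the wrong-dose category of important deviations in SAP 9.2.3.

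**Working it through.** **Inputs.** Cycle length 28 days (6.4.2), so the next cycle is due on Day 29. Delay limit 3 weeks (6.4.3), so the last permitted start is Day 29 + 21 = Day 50. Each non-recovery step takes 14 days (Table 6-8). Lenalidomide levels are 25, 15, 10 and 5 mg (Table 6-5), given on Days 1 to 21 (6.3.2). MLN9708 is given on Days 1, 8 and 15 (6.3.1).

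**Formula.** For a rash starting on Day d (1 to 28) that never recovers, step k falls on Day d + 14(k − 1). It lies within the limit if d + 14(k − 1) ≤ 50.

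| Step | Time from onset | Drug to interrupt | Already held? | Within Day 50 if | Onset days past the limit |
|---|---|---|---|---|---|
| 1 | 0 | lenalidomide | no | any d | 0 of 28 |
| 2 | 2 weeks | MLN9708 | no | any d | 0 of 28 |
| 3 | 4 weeks | lenalidomide | yes | d ≤ 50 − 28 = 22 | 6 of 28 |
| 4 | 6 weeks | MLN9708 | yes | d ≤ 50 − 42 = 8 | 20 of 28 |
| 5 | 8 weeks | lenalidomide | yes | d ≤ 50 − 56 = −6, so never | 28 of 28 |

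Step 3 falls on Day d + 28, never earlier than Day 29. From there on the path always runs alongside 6.4.3.

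**Restart doses, onset on Day 1.** Lenalidomide is held on Day 1 and MLN9708 on Day 15, both within the cycle.

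- Recovery between Days 29 and 43 (after step 3): Table 6-8 gives lenalidomide 10 mg, two levels below 25 mg, and nothing for MLN9708. Section 6.4.3 gives one level down: lenalidomide 15 mg and MLN9708 Level 1.
- Recovery between Days 43 and 50 (after step 4): Table 6-8 gives MLN9708 Level 2 and nothing for lenalidomide. Section 6.4.3 again gives one level down for each.
- Recovery between Days 15 and 29 (after step 2): Table 6-8 gives MLN9708 Level 1 and nothing for lenalidomide, which is also on hold.

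**Size for one subject.** A full cycle at 25 mg is 21 × 25 = 525 mg. At 10 mg it is 210 mg, or 210/525 = 40%. At 15 mg it is 315 mg, or 315/525 = 60%. Section 6.5.2.1 forbids re-escalation, so the difference carries into later cycles. Relative dose intensity, which uses the initial dose as denominator, shows it. Dosing compliance does not if the reduced dose counts as the scheduled level: it is 100% under either rule when every dose is taken.

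**The case against.** The strongest reply is that 6.4.3 already sits over Table 6-8. It takes interruptions made under 6.5 as its input, gives next-cycle starting doses for both drugs, and ends treatment at the limit. Table 6-8 has no stopping rule and does not authorise a new cycle. Ladder rows that non-recovery cannot reach in time remain usable through recurrence, and ordering a hold on a held drug does no more than leave it held.

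Much of this stands. A reader might infer that the two rules give opposing orders on discontinuation; they do not, because only 6.4.3 and 6.6.2 end treatment and they can be read as a cap. A reader might also infer that the 10 mg restart contradicts the one-level sentence in 6.5.2.3.1. It does not: that sentence covers recovery within 2 weeks, and the 15 mg row agrees with it. The conflict is with 6.4.3. Reading 6.4.3 as a cap settles when treatment ends, but leaves two different restart doses for recovery inside the window.

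Two provisions allow flexibility. Section 6.5.2.3.1 permits both drugs to be held or reduced in severe situations after discussion with the sponsor, and Table 6-10 allows lenalidomide to be held or discontinued for Grade 2 or 3 rash. Neither states a restart dose or an order of precedence.

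The overseas report in 1.4.2, that 3 of 6 patients at 2.97 mg/m² plus Rd had Grade 2 and 3 rash and had to discontinue lenalidomide, might be taken as the frequency of this problem. It gives no duration of rash, and 1.5.1 describes the rash as transient.

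**Conclusion.** The point holds for dosing. On the non-recovery path, three of the five Table 6-8 steps (3, 4 and 5) act on a drug already held, and each recovery row from step 2 on leaves the other held drug unaddressed. Where step 3 or 4 is reached inside the 3-week limit, the table and 6.4.3 can give different restart doses that cannot both be followed. In the Day 1 example this is 10 mg against 15 mg of lenalidomide, or 40% against 60% of the starting dose over a full cycle.

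This rests on three conditions. The rash must be related to MLN9708 or Rd and above Grade 1 or baseline, because 6.4.2 applies only then; Table 6-8 has no relatedness condition. It must remain unresolved for at least 4 weeks, for which the documents give no frequency. The comparison is cleanest for onset on Day 1. With later onset, step 2 comes after the last MLN9708 dose of the cycle (Day 15), so whether MLN9708 counts as interrupted in that cycle is itself open.

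The reach is limited to MLN9708 and lenalidomide dosing and the descriptive exposure summaries in the Rd cohorts from Cycle 2. With 3 to 6 subjects per cohort, one affected subject is 17% to 33% of a cohort (1/6 to 1/3). DLT assessment, which ends at Cycle 2 Day 1, is untouched, and neither rule sets the dexamethasone dose.

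**What to change.** Split Table 6-8 into a recurrence sequence and a non-recovery sequence. In the non-recovery sequence, state for each recovery row the status of both held drugs, and refer to 6.4.3 and 6.6.2, saying whether the 3-week limit ends the sequence. Bring the sentence in 6.5.2.3.1 that sends only repeat rash to the table into line with what the table covers. The restart doses in 6.4.3, 6.5.2.3.1 and Table 6-8 must be reconciled; which dose rule applies is for the sponsor to decide.

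The cost is one revised table and a few cross-references in a protocol amendment. No sample size, endpoint or analysis method changes.
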